5.2 Characteristics and Source of Supply

All medicinal products are provided by Ferring Pharmaceuticals and will be handled according to the principles of Good Manufacturing Practice (GMP).

5.2.1 Investigational Medicinal Product

5.2.1.1 Sodium Picosulfate, Magnesium Oxide and Anhydrous Citric Acid (NaP/MC) Oral Solution

NaP/MC Oral Solution will be supplied in two (2) 160-mL bottles and contains the following active ingredients:

- Sodium Picosulfate 10.0 mg
- Magnesium Oxide, Light 3.5 g
- Citric Acid, Anhydrous 12.0 g

Magnesium oxide and anhydrous citric acid react in solution to form magnesium citrate.

NaP/MC Oral Solution is manufactured and supplied by Ferring Pharmaceuticals in boxes containing two 160 mL bottles each.

5.2.1.2 PREPOPIK[®]

PREPOPIK[®] is a white crystalline powder for oral solution and will be supplied in two (2) packets. Each packet of PREPOPIK[®] contains the following ingredients:

- Sodium Picosulfate 10.0 mg
- Magnesium Oxide, Light 3.5 g
- Citric Acid, Anhydrous 12.0 g

Magnesium oxide and anhydrous citric acid react in solution to form magnesium citrate.

PREPOPIK[®] is manufactured and supplied by Ferring Pharmaceuticals for the U.S. market in boxes containing two packets and a dosing cup.

5.3 Packaging and Labeling

Packaging and labeling of the IMPs will be performed under the responsibility of the Ferring IMP department. All packaging and labeling operations will be performed according to the requirements of GMP and national regulatory requirements.

The IMPs will be labeled with trial-specific labels, and the content on the labels will be in accordance with ANNEX 13, EudraLex volume 4, and national requirements in the countries where the study will

be conducted. The labels will contain a self-adhesive tear-off portion to be affixed to the dispensing log maintained at the trial site.

5.4 Conditions for Storage and Use

The Investigator will ensure that the medicinal products will be stored in appropriate conditions in a secure location with controlled access. The storage compartment shall be monitored regularly and the temperature shall be documented. Deviations in storage temperature must be reported to Ferring without delay and the IMPs must not be used until further instructions are received.

5.4.1 Investigational Medicinal Product

NaP/MC Oral Solution should be stored in the original package at temperatures not exceeding 25°C (77°F) and protected from light.

PREPOPIK[®] should be stored in the original package at temperatures not exceeding 25°C (77°F) and protected from light.

5.5 Blinding / Unblinding

5.5.1 Blinding

Treatment is blinded to the endoscopist performing the colonoscopy and assessing the efficacy of the tested preparations and his/her assistant(s). Prior to the start of the study, the investigator will assign a coordinator and a pharmacist (if applicable) to act as the unblinded coordinator and unblinded pharmacist (if applicable). The designated unblinded study coordinator or unblinded pharmacist (if applicable) will be responsible for distribution and accountability of the drug and will instruct the subject and his/her parent/guardian about the use of the bowel preparation, including dietary restrictions.

5.5.2 Unblinding of Individual Subject Treatment

Emergency unblinding will be available to the investigator and designated persons at Sponsor via a centralized randomization system. In addition, one set of emergency decoding envelopes will be available at Sponsor as a back-up for unblinding.

Breaking of the blind in individual subjects is only permitted in case of a suspected unexpected serious adverse reaction (SUSAR) or in case of an important AE where the knowledge of the investigational product in question is required for therapeutic decisions for the management of the subject.

As far as the emergency permits, the need to break the blind will be agreed by the investigator and the sponsor. It should be recorded in the source documentation that the blind is broken, why, when, and by whom. In case of accidental unblinding (e.g., the subject tells the assessor), the same documentation as

for emergency unblinding must be obtained and the event must also be recorded in the source documentation.

It may be necessary to unblind an individual subject's treatment for the purposes of expedited reporting to the authorities or to the site's Institutional Review Board (IRB), or both. In that situation, every effort will be made to maintain blinding of sponsor personnel involved in data analysis and interpretation. Other personnel may be unblinded for SUSARs, including trial site staff as well as staff acting on behalf of Ferring. Information on whether the blind has been broken for any subjects must be collected before the database is declared clean and is released to the statistician.

5.6 Treatment Compliance

5.6.1 Dispensing and Accountability

IMP will be dispensed only to subjects who meet the eligibility criteria and are randomized to a treatment group in the trial. The unblinded coordinator or unblinded pharmacist (if applicable) (or his/her designated personnel, e.g., trial nurse) will maintain a Drug Dispensing Log detailing the dates and quantities of IMP dispensed to, and used by, each subject, as well as the unique batch identifier used in the trial. The unblinded monitor will verify the drug accountability during the trial and will document any discrepancies.

5.7 Assessment of Compliance

Subjects will be considered compliant if dosing occurs within ± 30 minutes of specified timings. The time of administration will be recorded in a subject diary. This diary will be provided to the subject by the unblinded coordinator or unblinded pharmacist who dispenses the drug. The subject diary and specified medication time periods will be documented in the eCRF by the unblinded coordinator during the procedure at Visit 3. The sponsor and the blinded endoscopist will not have access to this information during the trial.

5.8 Return and Destruction of Medicinal Products

All used medicinal products can be destroyed at the trial site (in accordance with local requirements) after drug accountability has been finalized, verified by the unblinded monitor, and signed off by the unblinded coordinator or unblinded pharmacist (if applicable).

All unused medicinal products must be returned for destruction, as instructed by the Ferring IMP department, after the drug accountability has been finalized, verified by the unblinded monitor, and signed off by the unblinded coordinator or unblinded pharmacist (if applicable). Products will be destroyed in accordance with local requirements.

6 TRIAL PROCEDURES

6.1 Screening Visit (Visit 1)

Prior to or at the Screening Visit, the subject must receive a detailed explanation of the study and must sign the Informed Consent Form after having sufficient time to consider his/her participation in the study. After the subject has signed the Informed Consent Form, the following will be performed:

- Obtain a thorough medical history and record demographic data
- Document any concomitant medications up to seven days prior
- Measure body weight and height
- Measure orthostatic vital signs (blood pressure and pulse)
- Perform a complete physical examination
- Obtain central laboratory sample: chemistry hematology and coagulation
- Urinalysis
- Serum pregnancy test for females of childbearing potential
- Conduct an ECG
- Schedule date of colonoscopy (≤ 21 Days from V1)
- Schedule Randomization Visit (V2, see Section 6.2): date of randomization ($V2 \leq 03$ days from V3)

6.2 Randomization Visit (Visit 2)

Randomization Visit 2 (V2) takes place ≤ 10 days from the Procedure/Colonoscopy Visit. For **females of childbearing potential**, the Randomization Visit (V2) **must occur within three (3) days prior to the colonoscopy** procedure. Females of childbearing potential **must** have a **negative urine pregnancy test** result at randomization. For males and postmenopausal women, the Randomization Visit (V2) must occur ≤ 10 days prior to the colonoscopy procedure (see Section 6.3). The following will be performed:

If the study screening requirements are met:

- Confirm eligibility
- Measure orthostatic vital signs (blood pressure and pulse)
- Measure body weight

- Urine pregnancy test (onsite) for females of childbearing potential (For females of childbearing potential randomization **must occur within three (3) days** prior to the colonoscopy procedure. Females of childbearing potential **must** have **a negative urine pregnancy test** result at randomization within 3 days prior to the colonoscopy.)
- Assign Subject Randomization number
- Dispense study medication
- Instruct the subject how to self-administer the study medication and provide them with a Subject Diary Card and detailed information, complete with assigned times of drug administration
- Provide the Acceptability and tolerability questionnaire to be completed prior to the procedure Visit (V3)
- Adverse events (recorded by study personnel)
- Document any new concomitant medications

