3.6.2 Selection of Endpoints

NI of split-dose NaP/MC Oral Solution to PREPOPIK[®] in overall colon cleansing in preparation for colonoscopy will be assessed by a blinded endoscopist using the Modified Aronchick scales ([Appendix C](#)) as the primary endpoint in this study. Results will be expressed as a proportion of subjects classified as responders, i.e., “excellent” and “good” according to the Modified Aronchick Scale (see [Appendix C](#)).

Efficacy of right, transverse, and left colon cleansing will be assessed by the blinded gastroenterologist using the Boston Bowel Preparation Scale (BBPS) ([Appendix C](#)).

Subject tolerability and satisfaction with the bowel cleansing preparation will be assessed by the validated³ Mayo Clinic Bowel Preparation Questionnaire ([Appendix D](#)), administered to subjects on the day of the colonoscopy and prior to the procedure.

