3.6.5 Selection and Timing of Dose for Each Subject

For each treatment arm, the first dose is administered the evening before the colonoscopy between 5:00 and 9:00 PM. The second dose is administered the next day at least 5 hours but no more than 9 hours prior to the colonoscopy.

Each subject will be randomly assigned to one of the following treatments:

- Split-dose Low-Volume NaP/MC Oral Solution
- Split-dose Low-Volume PREPOPIK[®]

Complete dosing and timing instructions for the study drugs are found in Section 0.

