6.3 Procedure/Colonoscopy Visit (Visit 3)

If the subject is participating in the PK subset, additional laboratory samples will be obtained for sodium picosulfate and BHPM at the following timepoints:

- 15 minutes before the second dose of IMP
- 1 to 2 hours after the second dose of IMP
- 3 to 6 hours after the second dose of IMP

Immediately prior to the colonoscopy, a PK sample will be obtained for **all participating subjects** in the study (approximately 2 hours prior to the colonoscopy).

Before the colonoscopy, the following will be performed:

- Treatment completed
- Collect Subject Diary Card
- Collect the Acceptability and tolerability completed questionnaire*
- Obtain orthostatic vital signs (blood pressure and pulse)
- Measure body weight
- Obtain laboratory sample (chemistry, hematology)
- Adverse events (recorded by study personnel)
- Document any concomitant medications

- PK subset only: PK samples for sodium picosulfate and BHPM 15 minutes before the second dose, and 1 to 2 hours and 3 to 6 hours after the second dose of the IMP
- All subjects: PK sample immediately prior to colonoscopy (approximately 2 hours prior to the colonoscopy)
- Perform study drug accountability by the unblinded coordinator or unblinded pharmacist (if applicable)

*Subjects should be instructed to fill out the questionnaire during the visit in a private area prior to contact with the Investigator and to return the completed questionnaire to the study coordinator. If the coordinator is not available during the procedure, the subject will put the completed questionnaire in a sealed envelope and provide it to a member of the surgical team. The study coordinator should check each questionnaire for completion, and if the subject did not answer all/some of the questions, note the reasons on the first page of the questionnaire. No one (including study coordinator or a family member) should interpret questions or response choices for the subject.

During the colonoscopy procedure, the blinded endoscopist will:

- Video-record the colonoscopy
- Use the Modified Aronchick Scale (see [Appendix C](#)) to score the quality of the bowel preparation in the overall colon after use of the study drug
- Use the Boston Bowel Preparation Scale (see [Appendix C](#)) to score the quality of the preparation in the different segments of the colon after use of the study drug
- Record the outcome of the colonoscopy

After the colonoscopy procedure, the following will be performed/recorded:

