7.1.3 Mayo Clinic Bowel Preparation Tolerability Questionnaire

A secondary efficacy endpoint will be assessed by the validated³ Mayo Clinic Bowel Preparation Tolerability Questionnaire. This questionnaire will be administered to the subject at Visit 3 on the day of the colonoscopy procedure. The Mayo Clinic Bowel Prep Tolerability Questionnaire is a simple, comprehensive questionnaire developed to evaluate the tolerability of various types of bowel preparations. The Mayo Clinic Bowel Preparation Tolerability Questionnaire is attached as [Appendix D](#).³

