## Appendix 4 Mayo Clinic Bowel Prep Tolerability Questionnaire

Mayo Clinic Bowel Prep Tolerability Questionnaire	

• Please, fill this questionnaire the morning of your colonoscopy procedure

• Please mark (for example ✓) the most appropriate response according to your current experience with the bowel preparation.

• Please, return this questionnaire at the front desk in the Gastroenterology department when you check-in for your procedure.

	

Patient name: \_\_\_\_\_

Age: \_\_\_\_\_

Gender:  Male  Female

Bowel prep: \_\_\_\_\_

Regimen:  PM only (single dose)  PM/AM (split dose)

1. How many bowel movements did you have in the week prior to starting colon preparation?

- 3 or less/week
- 4 to 8/week
- 9 or more/week

2. How much of the bowel preparation solution was left in the bottle after drinking it to your best effort?

- Less than 25%
- 25% - 50% left
- 50% - 75% left
- 75% or more left

3. How tolerable did you find the bowel preparation?

- Easy
- Acceptable
- Somewhat difficult
- Very difficult
- Unacceptable

4. Based on your current experience, would you be willing to drink the same preparation again if you need another colonoscopy in the future?

- Not willing at all
- Somewhat willing
- Mostly willing

5. In case you have experienced some difficulties in tolerating the bowel preparation, do you think that was due to your current health issues? (Check more than 1 option if applicable)

- Yes
- No
- It does not apply to me (I did not have any difficulties tolerating bowel preparation)
- It does not apply to me (I do not have any health issues)

©2014 Mayo Foundation for Medical Education and Research. All rights reserved. MCI7410

6. How much the following symptoms bothered you during bowel preparation?

Symptoms	None	Mild	Moderate	Severe
Bad taste in your mouth	1	2	3	4
Gastric fullness	1	2	3	4
Lack of sleep from excessive bathroom trips	1	2	3	4
Nausea/vomiting	1	2	3	4
Bloating/abdominal distention/gas	1	2	3	4
Abdominal pain/cramps	1	2	3	4
Headache	1	2	3	4

Others (please specify the symptom (s) and indicate how bothersome it was):  
\_\_\_\_\_  
\_\_\_\_\_

7. Is this your first colonoscopy procedure?

- No (please, answer the following questions)
- Yes (end of the questionnaire)

8. Which type of bowel preparation did you take in your previous colonoscopy?

- GoLyteley (1 gallon tasteless/salty solution)
- Moviprep (1/2 gallon flavored solution)

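### Protocol 6.2 hands out the tolerability questionnaire for completion before Visit 3, contradicting 6.3, 7.1.3 and the schedule tables, and a form dated the day of colonoscopy cannot be placed before or after the second dose

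*Protocol*

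**What the plan says.** Protocol 6.2 lists, among the tasks of the randomization visit, "Provide the Acceptability and tolerability questionnaire to be completed prior to the procedure Visit (V3". That visit can be well ahead of the procedure: "Randomization Visit 2 (V2) takes place ≤ 10 days from the Procedure/Colonoscopy Visit" (three days for women of childbearing potential).

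Protocol 6.3 has two entries. The list of steps before the colonoscopy says "Collect the Acceptability and tolerability completed questionnaire", which reads as if the form arrives already filled in. The footnote to that entry says "Subjects should be instructed to fill out the questionnaire during the visit in a private area prior to contact with the Investigator". It also has the coordinator check each form for completeness and bars everyone, family members included, from explaining the questions.

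Protocol 7.1.3 says "This questionnaire will be administered to the subject at Visit 3 on the day of the colonoscopy procedure". Protocol 3.6.2 says "administered to subjects on the day of the colonoscopy and prior to the procedure", and 10.3 agrees. The schedule tables (protocol synopsis, Protocol 6.7 Table 1, SAP Table 1) mark the questionnaire at Visit 3 only. Their Visit 2 dispensing row names the diary and the study medication, not the questionnaire.

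The two copies of the form differ. Protocol Appendix D asks only for completion before the procedure, and has a line for the date but none for the time. SAP Appendix 4 says "Please, fill this questionnaire the morning of your colonoscopy procedure" and has the form handed in at check-in.

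On dosing, Protocol 3.6.5 says "The second dose is administered the next day at least 5 hours but no more than 9 hours prior to the colonoscopy".

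**The concern.** A form cannot be completed both before Visit 3 and during it. Sites can therefore follow written text and still do different things, and two consequences follow.

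First, a form completed at home bypasses the 6.3 safeguards. In particular, the ban on anyone interpreting the questions cannot be enforced there.

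Second, 6.2 does not tie completion to the end of dosing. Protocol 9.6.3.4 names items 2, 3, 4, 6 and 9 for analysis: amount left, tolerability, willingness to repeat, symptoms, and comparison with a previous preparation. These ask about the preparation as a whole. A subject who answers after the first dose but goes on to take the second has rated only part of a split-dose regimen.

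The questionnaire is a named secondary endpoint, and Protocol 9.6.3.4 and SAP 9.3.4 compare it between arms with a Wilcoxon rank-sum test. Neither section has a rule on when a form must have been completed.

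**Working it through.** The plan gives no figure to reproduce. The check sets the instructions side by side and then places them on a time line.

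| Source | When or where completed | Tied to the last dose? |
|---|---|---|
| Protocol 6.2 | After Visit 2, before Visit 3 | No |
| Protocol 6.3, list | Collected complete before colonoscopy | Only by list order: completion of treatment comes first |
| Protocol 6.3, footnote | On site, during Visit 3 | As above |
| Protocol 7.1.3, schedule tables | Visit 3 | No |
| Protocol 3.6.2, 10.3 | Day of colonoscopy, before it | No |
| Protocol Appendix D | Before colonoscopy | No |
| SAP Appendix 4 | Morning of colonoscopy, returned at check-in | No |

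**Time line.** Let T be the start of colonoscopy.

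1. By Protocol 3.6.5, dose 2 falls between T−9 h and T−5 h, on the colonoscopy day.
2. By 6.2, the form can be in the subject's hands from as early as T−10 days. The period before Visit 3 therefore includes all the time before dose 2.
3. Most subjects could comply with 6.2 and still rate the full preparation. Assume that a subject outside the PK subset reaches the site at about T−2 h, the time of the PK sample taken in everyone (6.3). The gap between dose 2 and arrival is then 5 − 2 = 3 h to 9 − 2 = 7 h. Section 6.2 allows completion in that gap but does not require it.
4. The PK subset is different. Protocol 6.3 and 7.3 put its first sample, 15 minutes before dose 2, within Visit 3. The note under Figure 1 in 3.1.1 has these subjects in the unit on the day or night before. For them, completion before Visit 3, taken literally, means completion before dose 2. The subset is about 60 of 900 subjects: 60 / 900 = 6.7%.
5. The SAP copy does not close the gap. For an afternoon colonoscopy, the window from T−9 h to T−5 h lies at least partly in the morning, so a form completed that morning may come before or after dose 2.

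**What the data could show.** Dose times are recorded in the diary (Protocol 7.2.5) and transferred to the eCRF (5.7). The Appendix D form has a date.

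- Form dated before the colonoscopy day: it precedes any dose 2, and this can be seen.
- Form dated on the colonoscopy day: without a time, it cannot be placed before or after dose 2.

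**The case against.** Section 6.2 is the outlier. Every other section and table points to the day of colonoscopy or to Visit 3. The 6.3 list puts completion of treatment ahead of collecting the form, and item 2 asks how much was left after the subject's best effort, which presumes that drinking is over. The 6.2 wording may be a slip for completion before the procedure, which is what Appendix D says. Nothing tells a subject to answer after dose 1. All of this stands, and it is why few forms are likely to be affected. It does not remove the conflict, because a site following 6.2 is following the protocol.

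Four stronger readings are tempting, and the documents do not support them:

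- A reader might infer that forms completed on the evening of dose 1 would go unnoticed. They would carry the previous day's date. Only same-day forms are ambiguous.
- A reader might put a percentage on the dilution of any difference between arms. The documents give neither the share of forms completed early nor the part of any difference that arises from dose 2. If early completion differed by arm, the shift could go either way.
- A reader might argue that completion at home matters more because subjects know their arm. They know it wherever they complete the form, and completion under 6.3 is also private.
- A reader might say that every analysed answer is at risk. SAP 9.3.4 analyses all questions, including background items 1, 7 and 8 (earlier bowel habit, first colonoscopy or not, previous preparation), which do not depend on the timing of the doses.

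**Conclusion.** The contradiction between 6.2 and the rest of the protocol is real and should be corrected. Its practical consequence is a possibility that the text permits. It is not a demonstrated bias. Some forms may be completed off site without the safeguards, and some before the last dose. The second risk is most literal in the PK subset, about 6.7% of the trial, although the treatment-completed entry in 6.3 and the presence of these subjects on site work against it.

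The effect on the tolerability comparison cannot be calculated from the documents and is probably small. That judgement rests on most sites following 6.3 and the schedule tables. The primary endpoint, the right-colon test, the power and the type I error control are not affected, because tolerability is outside the testing sequence in Protocol 9.6.1 and SAP 9.1. The point still merits action: it concerns a stated procedure for a secondary endpoint compared between arms, and as designed the form cannot show which same-day answers preceded dose 2.

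**What to change.** 1. In Protocol 6.2, replace the instruction to give out the form with one to explain it only.
2. In 6.2, 6.3, 7.1.3, Protocol Appendix D and SAP Appendix 4, state one rule: the form is completed at Visit 3, after the last dose the subject actually takes and before the colonoscopy. Tying the rule to the last dose taken, and not to dose 2, matters because the mITT set includes anyone who took at least one dose. Subjects who stop after dose 1 never have a form completed after dose 2, and their answers bear directly on tolerability.
3. Add a completion time beside the date on the form.
4. In SAP 9.3.4, keep all mITT forms in the main analysis. Flag forms completed before the subject's last dose taken, using the diary dose times, and repeat the comparison without the flagged forms. Subjects who stopped after dose 1 stay in, provided their form follows that dose.

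The cost is wording in two documents, one field on an existing form and one repeated table. Treatment, sample size and the visit schedule do not change.
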